## Statistic analysis

The data will be expressed as a mean  $\pm$  SD. For continuous variables, the variations between the groups are compared by means of the averages calculated with the non parametric Wilcoxon and Mann-Whitney U tests. The variability of the biochemical parameters over time will be evaluated by means of tests for repeated measurements. A correlation analysis will be performed with the Pearson correlation test, after adequate logarithmic transformation of the parameters when necessary. Multiple regression analysis will be used to evaluate associations between variables. Statistical significance will be assumed for values of  $p < 0.05$ . All statistical analyzes will be performed with the SPSS program for Windows version 22.0 (SPSS INC; Chicago, IL, USA).

All children with T1D with disease onset in the years 2017, will receive omega 3 supplement (EPA + DHA 60 mg / kg / of), and will be compared from a metabolic point of view (in particular for the needs of insulin and glycated hemoglobin) according to the scheme outlined with the pre-supplementation data, deduced from the medical records retrospectively.

supplementation omega-3 ↓

Group 1 n.	Group 2 n.	Group 3 n.	Group 4 new onset	
	vs Group 1	vs Group 2	vs Group 3	
		vs Group 1	vs Group 2	
			vs Group 1	
2014	2015	2016	2017	2018

The analysis will allow to quantify the effects of omega-3 at different distance from the onset in terms of metabolic advantage (insulin units / Kg / die, glycated hemoglobin, etc.) and to evaluate if and how much supplementation after the onset may give metabolic advantages compared to other patients not yet supplemented.

Further statistical analysis could be performed if appropriate.

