Vitamin D and fatty acids Ω 3: role in the "honeymoon" of the Type 1 Diabetes of the child

The weight of diabetes on the child, on the family and in society

Type 1 diabetes (T1D) is an autoimmune disease in which there is a progressive reduction of insulin-secreting β -cells that involves the need to undertake replacement therapy with exogenous insulin.

The therapy consists of the administration of insulin in multiple administrations per day by pen or continuous infusion under the pump and requires frequent monitoring of capillary blood glucose or continuous glycemic monitoring with medical devices. T1D is burdened by important long-term complications: neurological, ocular, renal microangiopathic, which make diabetes the leading cause of chronic renal failure and dialysis, and acquired blindness. In addition, the pathology determines diabetic macroangiopathy, which leads to an increased risk of heart attack, macrovascular damage especially in the lower limbs with consequent diabetic foot and atherosclerotic complications of specific cardiac, cerebral and genital districts. These micro and macro-angiopathic complications, together with the continuous increase in the incidence and prevalence of diabetic pathology, cause a huge social and individual cost that currently represents a significant resource commitment, and will become an unsustainable health care expenditure in the years to come.

Data from the Pediatric Regional Register (0-15 years), reported in Literature, provide a precise assessment of the incidence of T1D in the Piedmont Region: from these data we can see an increase of 3.3% annually, with a consequent increase in direct costs of diabetes (in Italy for the NHS in 2012 direct costs over € 9 billion, 57% for hospital access, 30% for drugs and devices, 13% for outpatient care) and indirect and immaterial, which are even higher, even if hardly quantifiable. There was also a greater increase in incidence in pre-school and immigrant children, especially in relation to the dark color of the skin that limits the vitamin D biosynthesis.

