Usually the honeymoon phenomenon is exhausted within a year, even if a residual amount of secretion persists at least up to two years from the onset. The endogenous insulin secretion is quantifiable as C-peptide, which represents the conjugation peptide between chain A and B of pro-insulin, which after free cleavage in the portal circle molecules of C-peptide and insulin in molar ratio 1: 2. Unlike insulin that is rapidly degraded in the liver and tissues, the C-peptide passes the liver and is filtered by the unchanged renal glomeruli in the urine. C-peptide is not present in exogenous insulin of pharmacological origin. The endogenous insulin secretion is quantifiable as C-peptide. A persistence of C-peptide (also dosages 0.2 ng / ml) reduces the risk of complications, improves the metabolic compensation and reduces the number of hypoglycemic episodes, so at least one of its maintenance would be an important objective to preserve.

01/01/2017

The study is preliminary and aimed at identifying whether a therapy with Ω -3 could be of support in T1D especially in the first years of illness, when a persistence of a residual β -cell mass is presumable and it is possible to act better on the pro-inflammatory component (insulinitis).

Purpose of the study

The aim of the study is to evaluate whether a controlled administration of vitamin D and Ω -3, in the early years of the onset of T1D, can preserve the residual β -cell mass, evaluable with a reduced insulin need for a long time, with a persistent level of C-peptide, a lower glycemic variability compared to children who do not carry out this supplementation.

Secondary assessment is to perform a baseline assessment of the AA / EPA ratio in children with type 1 diabetes.

Subjects and Methods

The subjects will be recruited at the Diabetology Clinic of the Pediatric Clinic of the AOU "Maggiore della Carità" of Novara.

In particular, two groups of subjects will be included, subject to the signing of the informed consent:

1°,2°,3° the groups, with T1D onset in 2014, 2015, 2016, retrospectively were evaluated as historical controls before 2017.

4 group°: all children with T1D with disease onset in the years 2017, will receive omega 3 supplement (EPA + DHA 60 mg / kg / of), and will be compared from a metabolic point of view (in particular for the needs of insulin and glycated hemoglobin) according to the scheme outlined with the pre-supplementation data, deduced from the medical records retrospectively.

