1°,2°,3° groups: after 2017 were allowed to enter in the study and were prospectively evaluated

supplementation omega-3

Group 1	Group 2	Group 3	Group 4 new onset	
	vs Group 1	vs Group 2	vs Group 3	
		vs Group 1	vs Group 2	

			vs Group 1	
2014	2015	2016	2017	2018

The analysis will allow to quantify the effects of omega-3 at different distance from the onset in terms of metabolic advantage (insulin units / Kg / die, glycated hemoglobin, etc.) and to evaluate if and how much supplementation after the onset may give metabolic advantages compared to other patients not yet supplemented.

To the T0, T3, T6 and T12 will be detected anthropometric parameters (weight, height, BMI, Tanner Stages, PAOS / PAOD), insulin therapy in progress (IU / Kg / die) with MDI (multiple daily injection) or CSII (continuous subcutaneous infusion) and metabolic parameters (C-peptide, coagulation, lipid profile, basal blood sugar, glycated hemoglobin, vitamin D). The C-peptide in particular allows us to evaluate the residual cell function, which provides a "direct" measurement of endogenous insulin secretion. The fasting C-peptide / glycemia ratio will also be evaluated, as an estimate of residual insulin secretion. Glycated hemoglobin is an expression of blood sugar in the last three months. A value of less than 7.5% is a sign of good compensation.

In addition, the glucometer data will be downloaded at each visit to evaluate the glycemc variability parameters (mean glycemia, DS). A DS of less than 50% of the mean blood glucose represents an index of stability. The use by all patients of the same meter, delivered at the time of inclusion in the study, will eliminate the bias given by the diversity of the medical device. Indication will be given to perform pre-meal glycemc controls three times a day, and occasionally after 2 hours from the meal, in order to calculate the glycemc variability.

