An initial dosage of the blood levels of AA, EPA and DHA (and relative ratio) will be carried out by capillary sampling and application of a few drops of blood on absorbent paper for all subjects. Fatty acids are measurable in whole blood, with a lipidogram, in which each component of FFA is selectively differentiated, and then quantified the individual fractions. In particular we will evaluate the ratio between 20: 4 Ω -6 arachidonic acid (AA), precursor of pro-inflammatory cytokines, and EPA, precursor of anti-inflammatory cytokines; this ratio represents a balance between the effector pre-metabolites of inflammation, which determine the apoptotic degeneration of β -cells, and the anti-inflammatory ones, which preserve a cellular share with an insulin secretive function. This value AA / EPA <3 is proposed in Literature for adults or patients with other diseases, but has also been used for children.

The measurement will be carried out free of charge at the Department of Pharmacological and Biomolecular Sciences (DiSFEB), Faculty of Pharmaceutical Sciences, University of Milan.

An assessment of the dietary intake of EPA and DHA fatty acids will be carried out for all the subjects included in the study through an interview with the dietician and the compilation of a frequency food questionnaire. The collection of the food questionnaire will take place at the time of enrollment (T0) and 12 months after supplementation with omega 3. All healthy control subjects will be submitted to the food questionnaire. Nutritional indications will be given to all families in order to optimize an optimal dietary introduction of fatty acids as indicated by the LARNs.

Supplementation

The intervention under study is only the administration of omega-3, to all patients with onset in recent years (2014-2018) with a contribution of 60 mg / kg / day of the sum of EPA and DHA (corresponding respectively to acid eicosapentenoico and docaesoenoico). The AA / EPA ratio will be monitored (arachidonic acid, Ω -6 / eicosapentenoic acid Ω -3), to reach the optimal range <3 , as indicated in the literature.

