The chosen preparation will be omega-3, of extraction from fish, with a high concentration and purified to exclude mercury and lead, commercially available in stores and supermarkets. EnerZona. Equipe Enervit Srl will provide free Ener Zone, in capsules, from EPA 400 mg + DHA 200 mg, or capsules from EPA 200 mg + DHA 100 mg, or liquid solution, for subjects unable to swallow capsules or intolerant gluten capsules themselves; this will allow us to provide precise delivery and the same preparation to each patient.

All of our patients are supplemented with vitamin D. As vitamin D also has an immunomodulatory role it will be monitored in the study, and being frequently low at onset will be given at 1000 IU / day, as indicated in prophylaxis for children and adolescent; its level [as 25 (OH) D] will be controlled to reach the optimal values (established by Endocrine and other scientific societies) of 40-50 ng / ml, and possibly increased or reduced.

Inclusion criteria:

All children with autoimmune T1D, debuted in the years selected at the Pediatric Clinic of Novara. Some children with T1D in the wake of the published anecdotal case, have already spontaneously begun to supplement with omega 3, and will be excluded from the study. We have primarily considered our series of children with T1D onset according to the ADA, ISPAD and SIEDP criteria of the years 2015, 2016 and 2017, since insulin secretive activity persists for at least two years from the onset.

Exclusion criteria:

pathologies such as:

- coagulation defects
- renal diseases (nephrotic syndrome, calculosis, renal cysts, etc.)
- sarcoidosis, histoplasmosis

01/01/2017

- endocrinological diseases (hyperparathyroidism)
- tumoral pathologies or tuberculosis

Gluten intolerance (CD) or thyroiditis in T1D are not exclusion criteria.

Chronology of investigations and time of execution of the study

T.0 Signature of informed consent. Baseline auxological and metabolic evaluation (IU / Kg / day exogenous insulin) by means of examination, assessment of dietary intake through food questionnaire and interviews with dietician, blood tests (vitamin D, AA / EPA, C-peptide, basal glycemia, glycated hemoglobin, lipid profile, coagulation). Discharge of glucometer data for glycemic variability. Start supplementation with vitamin D, in case of deficiency, if subject not already supplemented. Begin supplementation with EPA + DHA, in case of deficiency, if willingness to recruit.

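### The onset-year cohort contrasts meant to quantify the omega-3 effect have only unadjusted rank tests assigned to them; the planned regression is not tied to them and names no covariates

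*SAP*

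**What the plan says.** The groups are defined by calendar year of onset. No randomisation, matching or stratification is described. In the protocol (Subjects and Methods), Groups 1-3 (onset 2014, 2015, 2016) "retrospectively were evaluated as historical controls before 2017", with data from medical records. The same groups "after 2017 were allowed to enter in the study and were prospectively evaluated". Group 4, with onset in 2017, is supplemented.

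The scheme in both documents lists six contrasts: Group 4 against each of Groups 3, 2 and 1, then 3 v 2, 3 v 1 and 2 v 1. Of these the SAP says: "The analysis will allow to quantify the effects of omega-3 at different distance from the onset".

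The method is the same in the Statistic analysis section of both documents. Between groups, "the variations between the groups are compared by means of the averages calculated with the non parametric Wilcoxon and Mann-Whitney U tests". The only multivariable method is one sentence: "Multiple regression analysis will be used to evaluate associations between variables". The SAP also leaves room for further analyses, without naming any.

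On who is supplemented, the protocol differs from itself. The Supplementation section has "The intervention under study is only the administration of omega-3, to all patients with onset in recent years (2014-2018"), and Subjects and Methods and the SAP say that all 2017-onset children receive it. The T.0 item of the Chronology section has "Begin supplementation with EPA + DHA, in case of deficiency, if willingness to recruit".

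**The concern.** When treatment follows the calendar year of onset, a comparison of cohorts mixes the effect of treatment with any other difference between the cohorts. A Mann-Whitney test cannot separate the two, and it gives no adjusted difference with a confidence interval.

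The documents give some reason to expect cohorts that differ:

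- On incidence, the opening section of the protocol reports: "There was also a greater increase in incidence in pre-school and immigrant children". Age at onset may therefore drift across cohorts.
- If the T.0 wording governs, supplemented children are selected by deficiency and willingness. If the other passages govern, they are not. These passages must be reconciled, because the answer decides which differences the analysis has to handle.

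At stake is the main message of the study. A difference in age or metabolic state at onset can appear as lower insulin need or better HbA1c under omega-3, or can mask a real benefit. Within-child (paired) contrasts are not affected by cohort case mix and are outside this point.

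**Working it through.** The plan states no sample size, SD, effect size or power (the group sizes are left blank in the SAP scheme), so there is no figure of its own to reproduce. The inputs are:

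- From the protocol: 3.3% annual growth in incidence. From the SAP: significance at 0.05 (two-sided assumed).
- Assumed: 20 v 20 children; total SD 0.25 IU/kg/day; correlation r between onset and follow-up value of 0.3, 0.5 or 0.7; equal SDs.
- SE of a raw difference = 0.25 x sqrt(2/20) = 0.0791.

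**1. Drift from the protocol's growth figure.** Three years of growth: 1.033^3 = 1.1023. Suppose every extra case is pre-pubertal and a share p was pre-pubertal before. The share then shifts by (1 - p) x 0.1023/1.1023 = 0.0464 (p = 0.5) or 0.0650 (p = 0.3). With an assumed pubertal difference in insulin need of 0.2-0.3 IU/kg/day:

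- bias = 0.2 x 0.0464 = 0.0093, up to 0.3 x 0.0650 = 0.0195 IU/kg/day;
- false-positive rate = P(|Z + bias/SE| > 1.96) = 5.2% to 5.7%.

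This source alone is negligible. It does not cover selection by deficiency or willingness.

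**2. How an onset difference D carries into the result.** If follow-up depends only on the onset value, a raw comparison carries r x D, a comparison of changes carries (r - 1) x D, and a model adjusted for the onset value carries 0.

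| r | raw | changes | adjusted |
|---|---|---|---|
| 0.5 | +50% | -50% | 0 |
| 0.7 | +70% | -30% | 0 |

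A simulation (4,000 runs, 20 v 20) gave +0.51 and +0.69, -0.51 and -0.32, and 0.00 and -0.02. The SAP does not say whether the variations it compares are follow-up values or changes, so even the sign of the bias is open.

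**3. Precision.** The 95% CI half-width is 1.96 x 0.0791 = 0.155 for raw values. It is multiplied by sqrt(2(1 - r)) for changes and by sqrt(1 - r^2) for the adjusted model.

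| r | raw | changes | adjusted |
|---|---|---|---|
| 0.3 | 0.155 | 0.183 | 0.148 |
| 0.5 | 0.155 | 0.155 | 0.134 |
| 0.7 | 0.155 | 0.120 | 0.111 |

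At r = 0.7 most of the gain is already obtained by comparing changes.

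**4. Missing onset values in control records.** Against raw values, the gain is lost at the missing share m that solves (1 - r^2)(1 + 1/(1 - m)) = 2. This gives m = 17% (r = 0.3), 40% (r = 0.5) and 66% (r = 0.7). It concerns precision only, not selection of complete records. Against changes there is no such loss, since changes also need the onset value.

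**5. Illustration of false positives.** A second simulation assumed no omega-3 effect and one covariate that differs by 0.5 SD between cohorts and correlates 0.5 with the outcome. Mann-Whitney rejected in 10.7%, 20.0% and 26.6% of runs at 20, 40 and 60 per cohort. The adjusted model stayed at 4.4-5.8% in all settings tried. The rate grows with sample size, so more children would not cure the problem. The 0.5 SD is an assumption, and the documents give no cohort characteristics.

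**The case against.** **Regression is already planned.** A reader might infer that the plan contains no adjustment at all. It does not go that far: regression is named and further analyses are allowed. What stands is that nothing ties the regression to the cohort contrasts or says what it adjusts for.

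**No material harm is shown.** This is largely right. The only estimate built on a protocol figure is negligible, and the larger rates rest on an imbalance that was assumed. The zero carry-over after adjustment also follows from an assumption. The case is for a better and cheap method, not for a demonstrated bias.

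**The contrasts among Groups 1-3 might be read as comparisons without omega-3.** The documents do not establish this. The protocol supplements onsets from 2014 to 2018, and the SAP speaks of effects at different distances from onset and of comparison with patients not yet supplemented. The scheme fits a staggered design in which, for example, Group 3 starts late and is compared with Group 1 at the same duration before supplementation. It also fits a plain list of all six pairs of four groups. Both readings are open.

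**Evidence that the cohorts differ can be overstated.** A reader might infer that controls from records underwent no selection. Subjects and Methods makes inclusion subject to consent, and children who took omega-3 on their own initiative are excluded, so this is not established. The background describes vitamin D use as becoming established, which suggests a change over time. But the Supplementation section says every patient of the clinic receives it, and the T.0 item starts it in deficient children not already supplemented. Past practice may have varied, but this is weak evidence.

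**The study is called preliminary.** That lowers the stakes. Its stated output is still an omega-3 effect judged at p < 0.05.

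**Conclusion.** The concern holds in this form: for contrasts between non-randomised cohorts that are meant to quantify an effect, the plan assigns only unadjusted tests and leaves its regression unspecified. This should be fixed, chiefly because the fix is cheap.

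The size and direction of any bias cannot be derived from the documents. Under the stated assumptions, 50-70% of an onset difference passes into a raw comparison (r = 0.5-0.7), and 30-50% passes with the opposite sign into a comparison of changes. Adjustment removes that part only, and only for covariates that are measured and correctly modelled. It does not remove willingness, calendar-time changes in care or other unmeasured differences. The documents do not support a claim that the planned results will be biased by a known amount.

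**What to change.** In the Statistic analysis section of both documents:

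- **Main analysis.** Make the planned regression the main between-cohort analysis for IU/kg/day, HbA1c and log C-peptide. Compare cohorts at matched time since onset, with supplementation, age at onset and that outcome's value at onset as terms. Report the adjusted difference (ratio for C-peptide) with a 95% CI.
- **Further covariates.** Add Tanner stage, sex and insulin regimen at onset only if the records of all cohorts hold them and group size allows.
- **Control time.** Count a child as a control only for observations before supplementation.
- **Groups 1-3.** State what each contrast compares. If later-starting supplemented children are compared with not-yet-supplemented children at the same duration, keep it as an omega-3 contrast. Estimate it separately by time from onset to start, or with an interaction, and adjust for the last pre-supplementation value (T0). A single supplementation term would pool early and late starts, which is the distinction the plan wants to study. Use a contrast as a check without omega-3 only if both sides are pre-supplementation.
- **Other tests.** Keep Mann-Whitney as a sensitivity analysis and paired tests for within-child contrasts.
- **Interpretation.** State that unmeasured and calendar-time differences remain and that results are associations.
- **Reconciliation.** Bring the passages on who starts omega-3 into agreement.

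The cost is some SAP wording and a short model in the software already named. The real cost lies in the control data. Values come from medical records, T0 for Groups 1-3 is study entry and not onset, and the T.3 and T.6 visits are for supplemented children only. Records without onset values are lost or need imputation, so check availability in every cohort before fixing the model.

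### The plan does not specify use of each child's own pre-supplementation value in the Group 2 vs 1, 3 vs 2 and 3 vs 1 contrasts, so these are less precise than the data allow

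*SAP*

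**What the plan says.** The Protocol (Subjects and Methods) states that the 2014, 2015 and 2016 onset cohorts "retrospectively were evaluated as historical controls before 2017". The group scheme then says that these cohorts "after 2017 were allowed to enter in the study and were prospectively evaluated". Under Supplementation, omega-3 goes "to all patients with onset in recent years (2014-2018". The chronology section requires insulin need, HbA1c and C-peptide at T0, when supplementation begins, and a re-evaluation of all subjects at T12.

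The scheme, repeated in the SAP, sets each cohort against the earlier ones, which gives six contrasts: 2 vs 1, 3 vs 2, 3 vs 1, and Group 4 vs 3, 2 and 1. The reference is "pre-supplementation data, deduced from the medical records retrospectively".

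For group differences the SAP states that "the variations between the groups are compared by means of the averages calculated with the non parametric Wilcoxon and Mann-Whitney U tests". Two further sentences could bear on the matter: "The variability of the biochemical parameters over time will be evaluated by means of tests for repeated measurements", and "Multiple regression analysis will be used to evaluate associations between variables". Neither is linked to a cohort contrast, and no baseline covariate is named. The threshold is p < 0.05. Sidedness, sample size, effect size, SD and within-child correlation are not given.

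**The concern.** A child in Group 2 or 3 who starts omega-3 has an own value from just before the start. A comparator from an earlier cohort may have unsupplemented chart values at the same two distances from onset. Insulin need, HbA1c and C-peptide can be expected to differ between children and to correlate within a child. A rank test on one later value per child leaves all of that variation in the error term.

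This is a single-centre study of yearly onset cohorts that sets out to quantify the effect at different distances from onset. If precision is given up, a real effect is more easily missed, and its size is estimated with wider error than the collected data allow. The issue is efficiency, not a false-positive problem.

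**Working it through.** **Inputs.** From the documents: alpha 0.05 and the contrasts above. Assumed, because the documents give nothing: two-sided test, normal outcome with SD 1, 12-30 children per group, effect 0.5-0.8 SD, and rho from 0.3 to 0.7 between a child's earlier and later values. The plan has no power figure to reproduce.

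**Step 1: variance.** Relative to the later value alone, adjusting for the child's own earlier value multiplies the error variance by (1 - rho²). A change score multiplies it by 2(1 - rho).

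| rho | ANCOVA | change score |
|---|---|---|
| 0.3 | 0.91 | 1.40 |
| 0.5 | 0.75 | 1.00 |
| 0.7 | 0.51 | 0.60 |

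A change score therefore gains nothing at rho 0.5 and loses at rho 0.3.

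**Step 2: power by formula.** With base power P, λ = 1.960 + z(P), and adjusted power = Φ(λ/√(1 - rho²) - 1.960). For P = 60% and rho 0.5: λ = 1.960 + 0.253 = 2.213; 2.213/0.866 = 2.556; Φ(0.596) = 72.4%, a gain of 12.4 points.

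| Base power | rho 0.3 | rho 0.5 | rho 0.7 |
|---|---|---|---|
| 50% | 53.8% (+3.8) | 61.9% (+11.9) | 78.4% (+28.4) |
| 60% | 64.1% (+4.1) | 72.4% (+12.4) | 87.3% (+27.3) |
| 80% | 83.6% (+3.6) | 89.9% (+9.9) | 97.5% (+17.5) |

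**Step 3: simulation against Mann-Whitney.** Bivariate normal earlier and later values, 4,000 trials per setting:

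| Per group | Effect (SD) | rho | Mann-Whitney, later value | ANCOVA | Gain (points) |
|---|---|---|---|---|---|
| 12 | 0.8 | 0.5 | 42% | 55% | 13 |
| 20 | 0.8 | 0.5 | 67.6% | 80.6% | 13.0 |
| 30 | 0.8 | 0.5 | 84% | 94% | 10 |
| 20 | 0.5 | 0.5 | 32% | 42% | 10 |
| 20 | 0.8 | 0.3 | 67.4% | 72.5% | 5.1 |
| 20 | 0.8 | 0.7 | 67.2% | 92.8% | 25.6 |

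Mann-Whitney on change scores at 20 per group and 0.8 SD gave 52.6%, 68.4% and 87.2% at rho 0.3, 0.5 and 0.7. Null rejection at rho 0.5 was 4.2-5.4% for all three methods. With 15-30 per group, effects of 0.6-0.8 SD and rho 0.5, the gain over Mann-Whitney was 9.2-14.6 points for ANCOVA and 7.6-10.8 for rank ANCOVA.

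Across 12-30 per group and 0.5-0.8 SD the ANCOVA gain is roughly 2-6 points (rho 0.3), 6-16 (rho 0.5) and 16-32 (rho 0.7). Each simulated power has a standard error of up to √(0.5 × 0.5/4000) = 0.8 points, so the ends of these ranges are approximate.

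**Step 4: are matched comparator values available?** Take T0 in January 2017.
- Group 2 is 12-24 months from onset at T0 and 24-36 at T12. Group 1 charts before 2017 reach 24-36 months.
- Group 3 is 0-12 months at T0 and 12-24 at T12. Group 2 charts reach 12-24 months, and Group 1 charts go further.

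With T0 in July 2017, Group 2 at T12 is 30-42 months from onset. A strict cut of comparator charts at the end of 2016 still stops at 24-36, so only 30-36 overlaps. If charts are used up to the comparator's own T0, also July 2017, they reach 30-42 months and the overlap returns.

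**The case against.** **A reader might infer that paired data are thrown away.** The text does not show that. Wilcoxon may mean the paired signed-rank test, variations may mean changes, and repeated-measures tests and regression are listed. What the text shows is that none of these is assigned to a cohort contrast. Nor would these readings recover the precision. A signed-rank test cannot compare different children, a before-after test within a child is confounded with disease duration, and change scores gain nothing at rho 0.5.

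**A reader might infer a clean one-way crossover.** The documents do not settle this. The Supplementation section covers all onset cohorts, whereas the chronology section makes starting EPA + DHA conditional on deficiency and willingness, and separates supplemented subjects (T3, T6) from all subjects (T12). These passages must be reconciled. How many children switch is unknown. The scheme's layout is also damaged in the text available, so which cohort is supplemented in each contrast is partly inferred.

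**A reader might take one figure, such as 10-13 points, as this trial's loss.** That holds only near rho 0.5 and mid-range power. Group 3 would have T0 within a year of onset, in the honeymoon period, where a low rho is plausible.

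**What else stands.** Each contrast compares different children, so Mann-Whitney is valid, and the study calls itself preliminary. Group 4 has no unsupplemented follow-up of its own, so three of six contrasts gain nothing. In non-randomised cohorts adjustment also moves the estimate: a baseline difference of 0.5 SD at rho 0.5 shifts it by 0.5 × 0.5 = 0.25 SD.

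**Conclusion.** The point holds as one of efficiency for Group 2 vs 1, 3 vs 2 and 3 vs 1. The only tests named for group differences are rank tests, and the T0 value, which is collected anyway, is not specified for use in these contrasts. The result is valid but less precise than it could be. The gain ranges in the working rest wholly on the assumed sample size, effect, rho and normal outcome. They also need comparator chart values at matched distances from onset, and the documents do not say how complete the charts are. The change is worth making because it is cheap. It does not show that the planned tests are wrong.

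**What to change.** **Change to the SAP.** For the three contrasts, specify ANCOVA of the T12 value on supplemented yes/no and the child's own T0 value, with a log transformation or rank-based ANCOVA if the outcome is skewed. Take comparator values from unsupplemented chart records at the same two distances from onset, and state whether those records run to the end of 2016 or to the comparator's own T0.

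**Alternative.** Fit a linear mixed model with a random intercept per child, distance from onset, and a time-varying supplementation term allowed to differ by distance from onset. This recognises a child who is first a control and later supplemented as the same child, and keeps the aim of estimating effects at different distances.

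Keep Mann-Whitney on the T12 value as a sensitivity analysis, and say which test serves which contrast.

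**Cost.** SAP wording, plus one earlier value per comparator from charts already under review. No new visits or tests.

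**Limits to state.** The Group 4 contrasts are not covered. Comparators without matched chart values drop out of the ANCOVA. Overlap depends on the actual T0 date. Adjustment shifts the estimate if cohorts differ at baseline, so unadjusted and adjusted results should both be shown. Calendar drift remains confounded with omega-3, as it is under the current tests.
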